9.2.1 Pre-study audit

The research center included in the study will be subject to a feasibility visit prior to center selection, where it will be verified that it meets the minimum requirements indicated by the sponsor.

9.2.2 Audit during the conduct of the study

They may take place at any time before, during, or after the conclusion of the study. If an audit or inspection is conducted, the investigator and the institution must agree to allow the auditor/inspector direct access to all relevant documents and must allocate their time and staff time to the auditor/inspector to discuss the findings and any pertinent issues. If the audit has not been scheduled by the sponsor, the center must notify Laboratorios Sophia, SA de CV immediately.

10. Sample size calculation and statistical analysis

10.1 Sample size calculation

The sample size calculation was based on the study's primary objective: to evaluate the safety and tolerability of PRO-185 ophthalmic solution (naphazoline hydrochloride 0.03% and hypromellose 0.2%) in clinically healthy subjects. To meet the study's primary objective, an estimated 22 subjects will contribute OA to the study.

10.1.1 Calculation methodology

A search was performed on the open access search engines PubMed (pubmed.ncbi.nlm.nih.gov) and Web of Science (webofscience.com), finding until May 2021, 102 results in PubMed and 24 in Web of Science that matched the search keywords: “*Naphazoline Ophthalmic*”. The extraction of this search was generated and the integrated database was reviewed, to eliminate duplicate matches and filter those articles that were in accordance with the objective of the study. After reviewing the *abstracts* (available only in 89 articles), 7 articles were chosen for their complete review (full text), of these, 5 articles were selected to make the proposal for the sample size [47, 48, 49, 50], one of them is a review article [51], this was used only as a reference. See appendix 16.3.

The mean \pm standard deviation (SD) sample size used in the selected studies was 24.4 ± 21.24 subjects (range, 6–60). Considering a 20% incidence rate for AEs, these values were entered into an online tool [52] to estimate sample size and power, following specific equations for the calculation [53]. Finally, the calculated value was increased by 20% to account for potential losses.

10.1.2 Size calculation

PRO-185 ophthalmic solution is expected to present in less than 20% of subjects any of the following AEs: increased IOP (>5 mmHg), heart rate changes (>15 bpm), increased systemic blood pressure (>15 mmHg in SBP or >10 mmHg in DBP), pharmacological mydriasis or grade 3 and 4 conjunctival hyperemia, 20 minutes after its application with respect to its initial value.

The sample size was calculated using the equation for a non-superiority proportion [53]. This equation is useful for non-inferiority/superiority tests, if we want to test whether a proportion (p) is not superior to a reference value, p_0 (20% in this case). The idea is that statistically significant differences between the proportion and the reference value cannot be of interest unless the difference is greater than a threshold δ (10% in this case). This type of calculation is useful in clinical studies where the value of δ is chosen based on clinical judgment and knowledge of the subject.

The hypothesis test is:

$$H_0: p - p_0 \leq \delta$$

$$H_1: p - p_0 > \delta$$

Equations

The calculation to estimate the sample size and power was performed using an online tool and following the equations [53]:

$$18 = p(1 - 0.2) \left(\frac{1.96 + z_{1-\beta}}{p - 0.2 - 0.1} \right)^2$$

$$1 - \beta = \Phi(z - 1.96) + \Phi(-z - 1.96), z = \frac{p - 0.2 - 0.1}{\sqrt{\frac{p(1 - 0.2)}{18}}}$$

Where:

n is the sample size (18)

p₀ is the reference value (0.20)

Φ is the function of the standard normal distribution

Φ⁻¹ is the function of the standard normal distribution

α is the Type I error (1.96)

β is the Type II error, which means that, 1-β (1-0.8) is the power

δ is the test margin (0.10)

According to the previous calculation, 18 subjects are estimated, increasing the calculation by 20% considering possible losses, 22 subjects are estimated to contribute OA to the study. This calculation is in accordance with the average number of subjects used in the clinical studies reviewed in the search performed in PubMed and Web of Science (24 subjects), where the incidence of adverse events was similar to that expected in this study.

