10.3.1 Population analysis

Statistical analysis will be presented to provide a general overview of the subjects enrolled in the study and an overview of the safety and tolerability of the results. Data provided by the research

site will be summarized for this purpose, according to their nature. The Shapiro-Wilk test will be performed to test whether the quantitative data are normally distributed.

The results of the quantitative variables will be presented as measures of central tendency: mean, standard deviation, maximum, and minimum. Changes in pupil diameter, BCVA, and body temperature will be expressed as continuous variables. Changes in IOP, HR, systemic blood pressure, TVL, and TF will be expressed as discrete variables.

The results of nominal and ordinal qualitative variables will be presented as frequencies, proportions, and/or percentages. For these, 2 x 2 frequency tables will be constructed. All percentages will be presented with one decimal place.

The level of difference considered significant will be an alpha (α) of 0.05 or less. The triangulation between the type of variable and the measurements is shown in Table 6 .

Table vi. Triangulation of concepts

Variable type	Variable	A1	A2	B1	B2	C1	C2	C3	C4	D1	D2	D3	D4	E1	E2
Selection															
A1	Demographics	DT													
A2	Medical history/Selection criteria		DT												
Basal															
B1	Vital signs		B	B		B		B	T				TM		
B2	Comprehensive ophthalmological evaluation		DTB		TB	B									
Security															
C1	PIO				B	B							TM		
C2	HR, SBP, DBP			B			B						TM		
C3	Pupillary diameter			B			B						TM		
C4	Conjunctival hyperemia			T				T					T		
Secondary Safety Outcome															
D1	AVMC				B					B			TM		
D2	Corneal and conjunctival stains			B						B			TM		
D3	Chemosis			T							T	T			
D4	Incidence of AE		TM	TM	TM	TM	TM	T	TM	TM	T	TM	TM	TM	TM
Exploratory															
E1	FR			B									TM	B	
E2	Body temperature		B										TM		B

Abbreviations: BCVA, best-corrected visual acuity; B, bivariate analysis; D, descriptive statistics; AE, adverse event; HR, heart rate; RR, respiratory rate; M, multivariate analysis; DBP, diastolic blood pressure; SBP, systolic blood pressure; IOP, intraocular pressure; T, 2x2 contingency table.

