### 4.1 Calculation methodology

A search was carried out in the open access search engines PubMed (pubmed.ncbi.nlm.nih.gov) and Web of Science (webofscience.com), finding until May 2021, 102 results in PubMed and 24 in Web of Science that matched the keywords of

Search: "Naphazoline Ophthalmic". The extract was generated from this search, and the integrated database was reviewed to eliminate duplicate matches and filter out those articles that were consistent with the study objective. After reviewing the *abstracts* (available only in 89 articles), 7 articles were selected for full-text review. Of these, 5 articles were selected to make the sample size proposal.

[2, 3, 4, 5], one of them is a review article [6], this was used only as a reference (see [Annex 9.1](#)).

The mean  $\pm$  standard deviation (SD) sample size used in the selected studies was  $24.4 \pm 21.24$  subjects (range 6–60). Considering a 10% proportion in the incidence of AEs, these values were entered into an online tool [7] to estimate the sample size and power, following the specific equations for the calculation [8].

Finally, the calculated value was increased by 20% to account for possible losses.

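### The 80% power behind n = 18 rests on a normal approximation with 1.8 expected events; a test that holds its error rate has 45% power at 18 subjects and 62% at 22

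*Protocol*

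**What the plan says.** Protocol 10.1.2 uses a one-proportion non-superiority equation from a textbook, run in an online tool. Its legend gives "n is the sample size (18"), "p₀ is the reference value (0.20"), "δ is the test margin (0.10") and "α is the Type I error (1.96"). Power is given as "β is the Type II error, which means that, 1-β (1-0.8) is the power". The true rate appears in the equations only as the symbol p; the text says that fewer than 20% of subjects are expected to have any of the listed events. The 18 is raised by 20% to 22.

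Protocol 10.3.1 adds: "The level of difference considered significant will be an alpha (α) of 0.05 or less". For conjunctival hyperemia, the one primary variable that the Protocol treats as qualitative, 10.3.2.1 plans a binomial chi-square test, with Fisher's exact test for small expected values.

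SAP 4.2 prints the same type of equation without numbers and gives no power value. SAP 4.1 says "Considering a 10% proportion in the incidence of AEs", where the parallel sentence in Protocol 10.1.1 uses 20%. The SAP hypotheses (3.2.1 and 3.2.2) also use 10%.

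Neither document gives an exact power calculation.

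**The concern.** The formula takes its variance at the assumed true rate and treats the observed proportion as normal. At a 10% rate and 18 subjects, 1.8 events are expected. The count then takes only a few likely values, its distribution is skewed, and the variance at 10% is less than half that at the 30% limit (0.09 against 0.21). A test whose error rate is held at the limit may have much less power than the formula reports.

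The calculation is the Protocol's formal justification for 22 subjects against the primary objective. If the power is overstated, a product with a true event rate of 10% would often fail to show a rate below 30%, and readers would misjudge what such a result means.

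**Working it through.** **Inputs.** From Protocol 10.1.2: p0 = 0.20, δ = 0.10 (limit 0.30), z = 1.96, n = 18, and 22 after the loss allowance. Power is taken as 0.80; read literally, the printed 1-0.8 is 20%. The true rate p = 0.10 is back-solved, not stated.

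**Reproducing the plan's figure.** The standard form is n = p(1-p)[(z_α + z_β)/(p - p0 - δ)]².

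- 0.10 × 0.90 × [(1.96 + 0.842)/(0.10 - 0.30)]² = 17.66, rounded up to 18.
- Formula power at 18: z = 0.20/√(0.09/18) = 2.83 in absolute value; Φ(2.83 - 1.96) = 80.7%. At 22 the formula gives 87.8%.
- The upper root, p = 0.62, also returns 18 but contradicts the expected rate below 20%.
- The Protocol prints the variance as p(1-0.2). In that form p = 0.10 gives 15.7, so 16, and 18 is returned at p = 0.107.

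**Exact binomial test of 30% against a lower rate, one-sided 0.025.** The cut-off is the largest event count whose lower-tail probability at 30% does not exceed 0.025.

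| n | Cut-off | Tail at 30% | Tail at 30% with one more event | Power at 10% |
|---|---|---|---|---|
| 18 | 1 | 0.0142 | 0.0600 | 45.0% |
| 19 | 1 | 0.0104 | 0.0462 | 42.0% |
| 20 | 1 | 0.0076 | 0.0355 | 39.2% |
| 21 | 1 | 0.0056 | 0.0271 | 36.5% |
| 22 | 2 | 0.0207 | 0.0681 | 62.0% |

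At 18 and 22 the cut-offs and powers are the same at one-sided 0.05, because the next tail exceeds 0.05. At 19 to 21 they are not: the cut-off becomes 2 and power is 71%, 68% and 65%. With p = 0.107, power at one-sided 0.025 is 41% at 18 and 58% at 22.

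**Score (binomial chi-square) test at z = 1.96.** The statistic is (x/n - 0.30)/√(0.21/n).

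- n = 18: -2.26 at 1 event, -1.75 at 2. Cut-off 1, power 45%.
- n = 22: -2.14 at 2 events, -1.67 at 3. Cut-off 2, power 62%.

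**Wald test at z = 1.96.** The variance is taken at the observed proportion.

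- n = 18: -2.55 at 2 events. Cut-off 2, power 73.4%, true one-sided error 6.0%.
- n = 22: -2.24 at 3 events. Cut-off 3, power 82.8%, true one-sided error 6.8%.

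**Size at which 80% is reached.** Exact power at one-sided 0.025 first reaches 80% at n = 31 (80.7%), falls below again from 32 to 35, and stays above from n = 36.

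**The case against.** The strongest objection is that the exact test is a substitution. The formula puts its variance at the assumed rate, so its natural companion is a Wald-type test. The power of that test is 73% at 18, a shortfall of 7 points, and 83% at 22, with no shortfall. This stands, so a reader should not infer that the 80% collapses to 45% for the very test the formula implies. What fails there is the error rate, which at 6.0% and 6.8% is more than double 2.5%. For a claim of safety, that error is in the wrong direction.

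The 2.5% itself is inferred from z = 1.96; the Protocol states only 0.05. At 18 and 22 this does not change the exact result. It does change the score test: at z = 1.645 it would accept 2 of 18 and 3 of 22, with the same 73% and 83% and the same error rates, which exceed even 5%.

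The true rate of 10% is not documented. The SAP's 10% is weak support, because the parallel Protocol sentence places the reference value there. If 10% is the SAP's reference, then p = 0.10 with a 10% margin gives 0.09 × (2.802/0.10)² = 70.6, so 71 and not 18. The figures here therefore belong to the Protocol's inputs. A reader might also infer that the SAP repeats the 80%; it prints no power value.

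The 45% may look pessimistic, since the primary analysis keeps everyone dosed (10.3.2.1) and 5.2.2 allows some replacement. That is fair, and 62% applies if all 22 are evaluable. But 18 is the number the plan was sized on, and missing data are not imputed (10.4).

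Finally, no section plans a claim of a rate below 30%. The Synopsis and 3.2 reject safety when any one event is observed in more than 20% of subjects, and the printed alternative points upward. At a 10% rate, power in that printed direction is practically zero. This limits the fix: the cut-offs cannot simply be added as a success rule.

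**Conclusion.** The concern holds for the power claim in Protocol 10.1.2. On the reading that returns 18 and fits the expected rate, a test that holds its error rate has 45% power at 18 subjects and 62% at 22, not 80%. With 19 to 21 evaluable subjects the exact test at one-sided 0.025 has 36% to 42%, so losing even one subject from 22 costs about 20 points or more. A Wald test comes near 80% only by exceeding its nominal error rate.

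This rests on a back-solved true rate of 10%, a limit of 30%, one comparison, and the aim of showing a rate below the limit. At a true rate of 10.7% the powers are 41% and 58%.

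Two stronger inferences are not supported. It is not an arithmetic slip, because the formula reproduces 18. Nor does it show that the trial must be enlarged: 22 subjects can still be reasonable for a phase I safety study, provided the power is described correctly.

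**What to change.** In Protocol 10.1.2:

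- State the assumed true rate and correct the printed power expression.
- Replace the 80% with the exact figures for a true rate of 10% against 30%: 45% at 18 and 62% at 22. Give the counts they rest on (at most 1 of 18, at most 2 of 22) and name the exact binomial test as the basis.
- Note that power is 36% to 42% at 19 to 21 evaluable subjects (one-sided 0.025).

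In the SAP, first align the reference rate and margin in 3.2, 4.1 and 4.2 with the Protocol. Then give the same figures in 4.2.

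Reconcile the direction and threshold of the decision rule in the Synopsis, 3.2 and 10.1.2 with this calculation. Until that is done, the counts explain the power and are not an added success rule. If the reconciled limit or true rate differs from 30% and 10%, recompute the figures.

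The power statement itself costs a few sentences in each document and no extra subjects or procedures. The stated power becomes less favourable. The reconciliation is a separate edit that the documents need in any case.

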1.1 Synopsis

Title of the study: Phase I clinical study to evaluate the safety and tolerability of PRO-185 ophthalmic solution applied in clinically healthy subjects	
Study number: SOPH185-0521/I	Creation date: 05/17/2021
Protocol version: 2.0	Version date: 27/07/2022
Therapeutic indication: Ocular vasoconstrictor	Use: Conjunctival hyperemia
Estimated duration of the study (from the first visit of the first patient to the preparation of the final report) : 5 months	Clinical development phase: Yo
Goals: Main objective: 
• To evaluate the safety and tolerability of PRO-185 ophthalmic solution in ophthalmologically and clinically healthy subjects. Specific objectives: 
• To evaluate the safety of PRO-185 ophthalmic solution by measuring the incidence of subjects experiencing an increase of >5 mmHg in intraocular pressure 20 minutes after application compared to the initial value.• To evaluate the safety of PRO-185 ophthalmic solution by measuring the incidence of subjects experiencing a heart rate variation of >15 beats per minute 20 minutes after application.• To evaluate the safety of PRO-185 ophthalmic solution by measuring the incidence of subjects with an increase in systolic blood pressure of >15 mmHg or >10 mmHg in diastolic blood pressure 20 minutes after application.	

- To assess tolerability by the incidence of grade 3 and 4 conjunctival hyperemia.
- To assess tolerability by the incidence of pharmacological mydriasis.
- Evaluate tolerability by the incidence of expected and unexpected adverse events.

Hypothesis :

H_0 = PRO-185 ophthalmic solution is safe and tolerable for ophthalmic use, as it occurred in 20% or less of subjects with any of the following adverse events: increased intraocular pressure (IOP >5 mmHg), heart rate variation (>15 bpm), increased systemic blood pressure [>15 mmHg systolic (SBP) or >10 mmHg diastolic (DBP)], pharmacological mydriasis, or grade 3 and 4 conjunctival hyperemia.

$$H_0: p - p_0 \leq \delta$$

H_1 = PRO-185 ophthalmic solution is not safe or tolerable for ophthalmic use because more than 20% of subjects experienced any of the following adverse events: increased IOP (>5 mmHg), heart rate variation (>15 bpm), increased systemic blood pressure [>15 mmHg systolic (SBP) or >10 mmHg diastolic (DBP)], pharmacological mydriasis, or grade 3 and 4 conjunctival hyperemia.

$$H_1: p - p_0 > \delta$$

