3.2 Hypothesis

H_0 = PRO-185 ophthalmic solution is safe and tolerable for ophthalmic use, as it occurred in 20% or less of subjects with any of the following adverse events: increased intraocular pressure (IOP >5 mmHg), heart rate variation (>15 bpm), increased systemic blood pressure [>15 mmHg systolic (SBP) or >10 mmHg diastolic (DBP)], pharmacological mydriasis, or grade 3 and 4 conjunctival hyperemia.

$$H_0: p - p_0 \leq \delta$$

H_1 = PRO-185 ophthalmic solution is not safe or tolerable for ophthalmic application because more than 20% of subjects experienced any of the following adverse events: increased IOP (>5 mmHg), heart rate variation (>15 bpm), increased systemic blood pressure [>15 mmHg systolic (SBP) or >10 mmHg diastolic (DBP)], pharmacological mydriasis, or grade 3 and 4 conjunctival hyperemia.

$$H_1: p - p_0 > \delta$$

Comparisons will be made between pre- and post-treatment measurements from visits 1 and 2, and between measurements from the baseline visit (before PT application) and measurements from the

final visit. Only one of the adverse event values described in the hypothesis need be abnormal with a frequency >20% between the comparisons (pre-treatment with post-treatment; or pre-PT baseline with values from the final visit) for the null hypothesis to be rejected.

4. Study design

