11.2 Amendments to the protocol

The amendment process will be relevant when there is a need to make any changes to a document that is part of the research project or protocol, due to changes in the methodological structure, replacement of the principal investigator, or the identification of risks to the research subjects.

Documents that may be amended include: the protocol, informed consent letter, researcher's manual, subject documents, measurement scales, and activity schedule.

Any amendment must be approved by the sponsor and/or the principal investigator. The amended document(s), once reviewed and approved by the Research Ethics Committee and the Research Committee or, when applicable, by the Biosafety Committee (entities that issued the initial favorable opinion for the conduct of the research), will be sent for authorization by the regulatory entity.

Amendments that substantially modify the protocol or impose additional or different risks to research subjects must be approved by the aforementioned Committees. It is the investigator's responsibility to take measures in situations requiring immediate action to prevent unnecessary harm to study participants.

The principal investigator is responsible for communicating to the Research Ethics Committee any amendments to the protocol that could affect the rights, safety, or well-being of the research participants. They must also report any situation or new knowledge that indicates an increased risk to the participants, the premature termination or suspension of the study, the reasons for this, and the results obtained to that point. They must also report the conclusion of the study upon completion of the research protocol.

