## 2. Introduction

This document describes the statistical analysis plan (SAP) designed for the SOPH185 protocol. 0521/I (Phase I clinical study to evaluate the safety and tolerability of PRO-185 ophthalmic solution applied to clinically healthy subjects). This PAE is intended to complement the study protocol. Any deviation from this document will be described in the Final Clinical Study Report [1].

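### Protocol 10.1.2 gives no true rate p; the reading that reproduces n = 18 joins the SAP's 10% to the Protocol's inputs, and its power is for showing p < 30%, not the worded 20% or 10% limit

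*Protocol*

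**What the plan says.** Protocol 10.1.2 sets a one-sample test of a proportion with a margin. It asks whether p "is not superior to a reference value, p_0 (20% in this case"), with δ = 10%, and prints H0: p - p0 ≤ δ against H1: p - p0 > δ. Both equations substitute 18, 0.2, 0.1 and 1.96 but keep p as a letter, and the list of symbols does not define p. The section's only statement about the rate is an expectation that it will be under 20%. The variance is printed as p(1-0.2). The value 1.96 is labelled the Type I error, and the power appears only in this form: "β is the Type II error, which means that, 1-β (1-0.8) is the power". The section concludes: "According to the previous calculation, 18 subjects are estimated, increasing the calculation by 20% considering possible losses, 22 subjects are estimated to contribute OA". Protocol 10.1.1 describes the input differently: "Considering a 20% incidence rate for AEs, these values were entered into an online tool".

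The worded hypotheses use a limit of 20%. The null in Protocol 1.1 reads "PRO-185 ophthalmic solution is safe and tolerable for ophthalmic use, as it occurred in 20% or less of subjects", and the alternative in 3.2 reads "PRO-185 ophthalmic solution is not safe or tolerable for ophthalmic application because more than 20% of subjects experienced". Both sections add that a frequency above 20% for a single listed event, in the comparisons described, is enough to reject H0.

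SAP 4.1 reports entering 10% for adverse events, and SAP 4.2 uses p(1-p), gives p0 no number and also arrives at 18, there described as per treatment arm. SAP 3.2 words the limit as 10% and places safety in H1, while printing the same inequalities as the Protocol. On how the two documents relate, SAP 2 says: "This PAE is intended to complement the study protocol".

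**The concern.** A sample-size statement should let a reader put the inputs in and obtain the number. Here the input that drives the result is missing, and the two documents report different rates for the tool (20% and 10%) with the same answer.

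The boundary in the formula is p0 + δ = 30%, a figure that no worded hypothesis contains. If the trial has few events, the report could say that the study was powered to show safety at the worded limit. The documents do not show that. The printed alternative also points towards too many events, whereas any power at a low true rate lies in the other direction.

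**Working it through.** **Inputs**
- n = 18, p0 = 0.20, δ = 0.10, z = 1.96: Protocol 10.1.2.
- Power 80% (z = 0.8416): inferred from the printed (1-0.8).
- p: 0.20 from Protocol 10.1.1, or 0.10 from SAP 4.1. Taking the SAP's 10% as p is an inference; the SAP does not call it p.
- Variance V: p(1-0.2) as printed in the Protocol; p(1-p) in SAP 4.2.

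**1. Reproducing 18**

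n = V × [(1.96 + 0.8416)/(p - p0 - δ)]², with (1.96 + 0.8416)² = 7.849.

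| p | V | n |
|---|---|---|
| 0.20 | 0.20 × 0.80 = 0.16 | 0.16 × 7.849/0.01 = 125.6, so 126 |
| 0.10 | 0.10 × 0.80 = 0.08 | 0.08 × 7.849/0.04 = 15.70, so 16 |
| 0.10 | 0.10 × 0.90 = 0.09 | 0.09 × 7.849/0.04 = 17.66, so 18 |

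The third row matches, and 18 × 1.2 = 21.6, so 22. Using one-sided 5% and 90% power with the Protocol's variance also rounds to 18 (17.13), again at p = 0.10 and p0 = 0.20, but it contradicts the printed 1.96. Reading the power literally as 20% with p = 0.20 gives 20.01, so 21.

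**2. What the power is for**

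At p = 0.10, p - p0 - δ = -0.20. With n = 18:
- V = 0.09: z = -0.20/√(0.09/18) = -2.828; lower tail Φ(2.828 - 1.96) = 80.7%.
- V = 0.08 (Protocol as printed): z = -3.000; lower tail 85.1%.

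The upper tail is below 0.0001% in both. The power is therefore for concluding p < 0.30, and p = 0.10 lies inside the printed H0. In the direction of the printed H1, n = 18 would need a true rate of 0.62 (with p(1-p)) or 0.84 (with p(1-0.2)), far from the expectation of under 20%.

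**3. The same formula against the worded limits, with V = p(1-p)**

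Limit 20%, p = 0.10:
- n = 18: z = -0.10/√(0.09/18) = -1.414; power 29%.
- n = 22: z = -1.563; power 35%.
- For 80%: 0.09 × 7.849/0.01 = 70.6, so 71.

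Limit 20%, other rates (assumed; neither document states them):
- p = 0.05: 0.0475 × 7.849/0.0225 = 16.6, so 17.
- p = 0.15: 0.1275 × 7.849/0.0025 = 400.3, so 401.

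Limit 10%, p = 0.10: the difference is zero, so no finite size exists.

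**4. Exact binomial, for illustration only**

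The documents specify no test against these limits. One-sided, true p = 0.10:
- n = 22, limit 20%: at 2.5%, reject only with 0 events, power 0.9^22 = 9.8%; at 5%, reject with 0 or 1 event (size 4.8%), power 33.9%.
- n = 22, limit 30%, at 2.5%: reject with at most 2 events (size 2.07%), power 62%.
- n = 18, at 2.5%: power 15.0% against 20% and 45.0% against 30%.
- n = 22, limit 10%: 0 of 22 has probability 9.8% when p = 10%, so no result can reject at 2.5% or 5%.

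**5. Precision of 22 subjects**

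Upper ends of the two-sided exact 95% interval: 15.4% for 0/22, 22.8% for 1/22, 29.2% for 2/22.

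**The case against.** The best defence is that the documents are meant to be read together, and together they give 18 exactly. Solving the Protocol's printed equation for n = 18 also gives p = 0.107, which fits its expectation of under 20%, so 126 is a weak reading of what was intended. The margin is not concealed either: Protocol 10.1.2 explains it, and the inequality stands beside the worded hypotheses. These points stand. They show that a sensible calculation probably lies behind the number, but they do not supply p or reconcile 30% with 20% or 10%.

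The joined reading is itself uncertain. The SAP's 10% could be a reference value, since SAP 3.2 and 4.2 also use it as a limit or upper bound. The SAP still carries SPSS 19.0 and the tests that the Protocol's change history replaced, so the two documents may reflect different stages of planning.

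A reader might infer that the trial is underpowered and must enrol 71. The documents do not support that: neither p nor the limit is settled, and 17 would suffice for a 20% limit at an assumed p of 5%. Nor is 9.8% the trial's power. It belongs to an assumed test at one level, changes to 33.9% at 5%, and owes much to discreteness: at 2.5% it is lower with 22 subjects than with 18.

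It is also fair to say that a phase I study needs no formal power. This plan nevertheless states a hypothesis and a power calculation, and they should agree.

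**Conclusion.** The concern holds as an inconsistency in the plan's own sample-size statement. The number 18 cannot be checked from the Protocol. On the reading that reproduces it with the printed 1.96, the design has about 80% power to show a rate below 30%, in the direction opposite to the printed H1 and for neither worded limit. Measured by the same formula at p = 10%, moving the limit from 30% to 20% lowers the power at 18 subjects from 80.7% to 29%.

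This rests on three assumptions: the SAP's 10% is p, the power was 80%, and p is a single proportion. The last is open, because the rejection rule in Protocol 1.1 and 3.2 works event by event and comparison by comparison on an observed frequency above 20%. The finding does not show that 22 subjects are too few for a phase I tolerability study.

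**What to change.** - In Protocol 10.1 and SAP 4, state the p, p0, δ, alpha and power actually entered in the online tool. Use p(1-p) in the size and power equations of both documents, label 1.96 as a z value, and print the power as 80% if that was the value used. Remove the reference to treatment arms from SAP 4.2.
- Make the inequality, the worded hypotheses and one limit L agree across Protocol 1.1, 3.2 and 10.1 and SAP 3.2 and 4. If the aim is to show safety, the form is H0: p ≥ L against H1: p < L, with L confirmed by the sponsor.
- State whether p is the composite of the listed events or each event separately, and over which comparison. Reconcile this with the single-event rule in Protocol 1.1 and 3.2; without it, any restated power is undefined.
- Then restate the power of the existing 22 subjects, and of 18 evaluable, for that limit and direction. Alternatively, present 22 as a precision-based size, using the interval limits above.

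The cost is one text amendment to both documents. Under Protocol 11.2 it goes to the committees and then "will be sent for authorization by the regulatory entity". The correction itself adds no subjects, visits or assessments, provided the sponsor accepts the restated power or the precision justification. The stated power is likely to become less favourable.
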